10.1 Sample size

Approximately 70 subjects will be enrolled with a goal that approximately 50 will be completed. Based on historical clinical data a sample size of 50 completing subjects is sufficient to detect a mean difference of 0.5 (0 – 10) in subjective ratings assuming $\alpha=0.05$ and a power of 80% (Table 3).

Table 3: Sample Size Calculations

Mean individual difference in score	Mean individual standard deviation	Sample size, Power 80% (p = 0.05)
0.5	1.2	48

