7.3.1 Visit 1: Screening / Baseline Visit / Dispensing Pair #1

Screening / Baseline

The following evaluations will be performed to assess eligibility according to the Inclusion and Exclusion Criteria at the Screening visit:

1. The subject is expected to attend the screening / baseline visit not wearing their habitual contact lens products for at least 12 hours prior to the study visit.
2. The subject will be required to read and sign an Informed Consent Form prior to enrolment. When the subject has signed the consent form, the subject will be considered to be enrolled on to the study.
3. Subject demographics and medical history (age, sex, race and ethnicity, medical conditions, medications, allergies) will be recorded by the investigator.
4. Contact lens history (own lens information, rewetting drop use, and wear time)
5. Baseline monocular high illumination, high contrast (HIHC) entrance distance (4m) visual acuity with habitual spectacles or spectacle refraction
6. Auto refraction/auto keratometry: Flat and Steep K readings (D)
7. Sphero-cylindrical refraction (D), monocular distance visual acuity (HIHC) (logMAR)
 - The endpoint of this refraction will be the best objective acuity, with (-) only being given with objective acuity, not subjective acuity improvement (not to the point that the letters start to shrink in size).
8. Slit lamp biomicroscopy will be assessed according to the guidelines set out in the CVI Grading scales (Appendix 1).
9. The investigator will confirm that the subject meets the criteria set out in the inclusion criteria, and none of the exclusion criteria and is eligible to continue in the study.
10. The subject will be assigned a randomization ID and the first pair of contact lenses will be selected according to the randomization table.
11. Initial contact lens power chosen based on vertexed, spherical equivalent obtained from refraction. The initial contact lens power will be kept the same for both study lenses (i.e. based on empirical powers).

Dispensing Pair #1

1. The lenses will be inserted by the subject from the blister pack. The use of saline for rinsing prior to insertion is permitted if necessary.

[REDACTED]

- a. [REDACTED]
- b. [REDACTED]
- c. [REDACTED]

[REDACTED]

4. [REDACTED]

5. [REDACTED]

- a. [REDACTED]
- b. [REDACTED]
- c. [REDACTED]

6. Monocular logMAR visual acuity (4M) will be recorded with high contrast letters under high and low room illumination*.

- a. [REDACTED]
- b. [REDACTED]

[REDACTED]

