7. The subject will be asked to give subjective ratings post lens settling

- a. Comfort (0-10 scale) and comments
- b. [REDACTED]
- c. [REDACTED]
- d. [REDACTED]

8. [REDACTED]

[REDACTED]

- [REDACTED]
- [REDACTED]
9. Monocular lens fit will be assessed and graded according to the CVI grading scales (Appendix 2). Lens fit will be video recorded in the event of poor fit.
 - a. Corneal coverage at all times (y/n)
 - b. Lens centration (optimal /slightly decentered, <0.5mm /extremely decentered >0.5mm, NTSI)
 - c. [REDACTED]
 - d. Post-blink movement (mm)
 - e. Primary gaze lag (mm)
 - f. Upgaze lens lag (mm)
 - g. Lens push-up tightness (%)
 - h. Overall lens fit acceptance (0-4 scale, and yes/no) and investigator reason, if unacceptable.
 - i. Overall lens fit impression (-2 to 2 scale)

10. The subject will be encouraged to wear the study lenses as much as they normally do with their habitual lenses and for a minimal of 5 days/week.

11. The subject will be instructed to discard study lenses at home nightly but to keep lenses with problem to return to the site.

12. The subject will be given enough contact lenses to wear until the next study visit.

13. The subject will be discharged and reminded to return for the one week visit of the first pair.

7.3.2 Visit 2: Follow-up Pair #1/Dispensing Pair 2

*Subjects will be asked to wear lenses for **at least 2 hours** prior to the visit appointment.*

Subjects who attend without lenses in situ for at least two hours will be rescheduled.

The following procedures will be performed (any ocular measurement procedures outlined below will be carried out on each eye):

[REDACTED]

- [REDACTED]
- [REDACTED]
- [REDACTED]
- [REDACTED]
- [REDACTED]

- Comfort at insertion, during the day, end of the day and overall comfort since the last visit (0-10 scale)

- [REDACTED]

2. [REDACTED]

- [REDACTED]
- [REDACTED]
- [REDACTED]
- [REDACTED]

[REDACTED]

4. [REDACTED]

- [REDACTED]
- [REDACTED] type
- [REDACTED]
- [REDACTED]

5. Monocular lens fit will then be assessed and graded according to CVI grading scales (Appendix 2).

- a. Corneal coverage at all times (y/n)
- b. Lens centration (optimal /slightly decentered, <0.5mm /extremely decentered >0.5mm, NTSI)
- [REDACTED]
- d. Post-blink movement (mm)
- e. Primary gaze lag (mm)
- f. Upgaze lens lag (mm)
- g. Lens push-up tightness (%)
- h. Overall lens fit acceptance (0-4 scale, and yes/no) and investigator reason, if unacceptable.

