10.2 Statistical analysis

Summary statistics will be produced (e.g. mean, standard deviation). Paired t test will be used to compare slit lamp biomicroscopy, lens fit and subjective scores between study lens types. Repeated Measures Analysis of Variance (ANOVA) or paired analysis will be used to compare the variables between study visits. The critical alpha level for statistical significance will be set at $p \leq 0.05$, with adjustment for multiple comparisons.

All participants who were evaluated will be used in the analysis. In the event of missing data, individual data points will be excluded in the analysis and not extrapolated from the collected data.

11 Data Quality Assurance

[REDACTED]

[REDACTED]

[REDACTED]

[REDACTED]

- [REDACTED]

- [REDACTED]

[REDACTED]

[REDACTED]

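### Section 10.1 states 80% power at an unadjusted alpha of 0.05, while the visible 10.2 judges significance after a multiplicity adjustment that it does not limit, so on its plain reading the stated power is not at the alpha used for an individual rating

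*Combined protocol and SAP*

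**What the plan says.** Section 10.1 sizes the trial on subjective ratings, in the plural. It says that "a sample size of 50 completing subjects is sufficient to detect a mean difference of 0.5" on a 0 to 10 scale, with alpha 0.05 and 80% power. Table 3 gives the inputs: mean individual difference 0.5, standard deviation 1.2, sample size 48. It mentions no allowance for multiple tests. On numbers, 10.1 says "Approximately 70 subjects will be enrolled with a goal that approximately 50 will be completed".

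Section 10.2 has two test sentences followed by one significance rule. The first test sentence is "Paired t test will be used to compare slit lamp biomicroscopy, lens fit and subjective scores between study lens types". The second is "Repeated Measures Analysis of Variance (ANOVA) or paired analysis will be used to compare the variables between study visits". The rule sets the critical level at p ≤ 0.05, "with adjustment for multiple comparisons". The visible text gives no family, method or number of tests, and exempts no rating.

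The follow-up procedures in 7.3.2 show four comfort ratings on the 0 to 10 scale: at insertion, during the day, at the end of the day, and overall. Other items there are redacted, as is the text of Section 2 (objective and hypothesis).

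**The concern.** The power statement and the significance rule should describe the same test. Section 10.1 describes a test at 0.05. Section 10.2 describes a test at 0.05 after an adjustment whose reach it does not state, although the between-lens subjective scores are among the comparisons listed in that section. If those scores fall under the adjustment, an individual rating is judged at a stricter level than the one behind the 80%.

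Section 10.1 is the only visible justification for 50 completers. As the two sections stand, a reader cannot tell at which alpha a rating will be judged, nor whether 80% describes the power for any particular rating.

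**Working it through.** **Inputs from the plan.** Difference d = 0.5, SD s = 1.2 and n = 48 (Table 3); 50 completers, alpha 0.05 and power 80% (10.1); paired t test between lenses (10.2). Sidedness is not stated. The SD is taken as that of the within-subject difference, because that reading reproduces the table.

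**Formula.** For a paired t test at two-sided level a, the non-centrality is δ = (d/s)·√n. Power = P(T > t) + P(T < −t), where T is non-central t with n − 1 degrees of freedom and non-centrality δ, and t is the 1 − a/2 quantile of central t with n − 1 degrees of freedom.

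**Step 1: reproduce Table 3** (a = 0.05).
- n = 47: δ = 0.41667 × √47 = 2.857, power 79.9%.
- n = 48: δ = 0.41667 × √48 = 2.887, power 80.7%.
- n = 50: δ = 0.41667 × √50 = 2.946, power 82.3%.

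So 48 is the smallest n that reaches 80%. The alternatives do not give 48: a one-sided t test gives 38, a two-sided normal approximation 46, and a parallel-group comparison 91 per arm. Table 3 is therefore one unadjusted two-sided paired test.

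**Step 2: how much adjustment 50 completers can absorb.** Solving power = 80% at n = 50 gives a = 0.0412. Any per-test level below that takes power for a 0.5 difference under 80%.

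**Step 3: illustrative adjustments.** Family size and method are assumptions, since the plan states neither. Four is the number of visible comfort ratings; the plan does not call them a family.

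| Bonferroni over | Per-test alpha | Power, n = 50 | Power, n = 60 | Difference detectable at 80%, n = 50 |
|---|---|---|---|---|
| 1 (none) | 0.05 | 82.3% | 88.8% | – |
| 2 | 0.05/2 = 0.025 | 73.5% | 82.0% | 0.537 |
| 4 | 0.05/4 = 0.0125 | 63.9% | 74.0% | 0.585 |

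**Step 4: less conservative methods.** Power for one rating at n = 50 was simulated with 40,000 trials per scenario, normally distributed differences, and a common correlation between ratings assumed at 0, 0.3, 0.5, 0.8 and 0.9.
- Two ratings, both differing by 0.5: Holm 78–80%, Hochberg 80–81%.
- Four ratings, all differing: Holm 71–75%, Hochberg 75–77%, Benjamini-Hochberg 78–80%.
- Four ratings, two differing: Holm and Hochberg 66–67%, Benjamini-Hochberg 70–71%.
- Four ratings, one differing: about 64% by each of these methods and by Bonferroni.
- First test in a fixed order: no loss, 82.3%.

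**The case against.** The strongest reply is that no contradiction has been shown. Section 10.1 is true on its own stated assumption, and the sentence immediately before the adjustment rule is the one on comparisons between visits. With two lenses, each rating has a single between-lens contrast, whereas repeated-measures comparisons are a usual place for such an adjustment. Separately, Section 2 is redacted and may name one rating tested at 0.05. Either situation would leave the 10.1 figure intact for a single rating, and the documents exclude neither. That part stands and makes the point conditional. It does not remove it: the rule is a separate sentence that sets the significance level after both test sentences, and nothing visible confines it to visits or exempts a primary rating.

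A second reply is that the size of the loss depends on an assumed family and method. That also stands. The figures above run from no loss to about 64%, and none is the plan's own.

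Third, 50 is a goal. Section 10.2 says "All participants who were evaluated will be used in the analysis", and 7.1 allows up to 80 recruits, so more than 50 may contribute. At n = 60, Bonferroni over two is back to 82.0%. However, enrolment is counted from consent (7.3.1: "When the subject has signed the consent form, the subject will be considered to be enrolled on to the study"), before eligibility is confirmed, so the 70 enrolled can include screen failures and are not 70 analysable subjects.

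Two stronger readings are tempting. A reader might infer that the trial is underpowered or that 50 completers are too few. The documents do not support that, because the scope of the adjustment, the method and the final number analysed are all open. A reader might also infer that a non-significant rating could not be interpreted. That goes too far: the estimated difference and its confidence interval would serve that purpose better than the planned power.

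**Conclusion.** The point holds in conditional form and should be fixed. It is certain that Table 3 contains no multiplicity allowance and that the only visible significance rule carries an adjustment of unstated scope. On the plain reading of 10.2, the 80% is therefore not stated at the alpha used for an individual rating. How far power falls cannot be fixed from the documents; Bonferroni over two or four ratings at 50 completers (73.5% and 63.9%) illustrates the scale, with a true difference of 0.5 and an SD of 1.2. Confidence is moderate, because the between-visit reading and the redacted Section 2 remain possible. The finding is a mismatch between two statements in the plan and leaves open whether the sample size is adequate.

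**What to change.** Make 10.1 and 10.2 use the same alpha, by one of three routes:

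1. If the adjustment applies across ratings, state the family and method in 10.2, and restate the power or detectable difference in 10.1 and Table 3 at the adjusted alpha. With Bonferroni over four and 50 completers, for example, that would be about 64% power for 0.5, or about 0.585 detectable at 80% power.
2. Otherwise, designate in advance one rating and one visit to be tested at two-sided 0.05 without adjustment. Section 10.1 names none at present. Say that the 80% applies only to that test, and apply the adjustment to the remaining comparisons.
3. If the adjustment was meant only for comparisons between visits, limit the 10.2 sentence to those.

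The cost is one or two sentences and no added subjects. The downside is a less favourable stated power under the first route, or no stated power for the other ratings under the second.

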10.2 Statistical analysis

Summary statistics will be produced (e.g. mean, standard deviation). Paired t test will be used to compare slit lamp biomicroscopy, lens fit and subjective scores between study lens types. Repeated Measures Analysis of Variance (ANOVA) or paired analysis will be used to compare the variables between study visits. The critical alpha level for statistical significance will be set at $p \leq 0.05$, with adjustment for multiple comparisons.

All participants who were evaluated will be used in the analysis. In the event of missing data, individual data points will be excluded in the analysis and not extrapolated from the collected data.

11 Data Quality Assurance

[REDACTED]

[REDACTED]

[REDACTED]

[REDACTED]

- [REDACTED]

- [REDACTED]

[REDACTED]

[REDACTED]

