CooperVision™

Study document: Protocol

**A DISPENSING CLINICAL TRIAL OF INVIGOR I DAILY DISPOSABLE LENS AGAINST
CLARITI 1-DAY LENS**

Sponsor Study Code:	CV-19-01
Version Number:	1.0
Implementation document Date:	17 December 2018
Sponsor Company:	CooperVision, Inc.
Document Type:	Protocol
Study Category:	██████████
Clinical Sites:	CORL, Indiana University Southern California College of Optometry

Study Sponsor Representative:

[Redacted Signature]

Date: [Redacted]

CooperVision Sponsor Management

[Redacted Signature]

Date: [Redacted]

Site Principal Investigator:

[Redacted Signature]

Date: [Redacted]

Site Principal Investigator:

[Redacted Signature]

Date: [Redacted]

TABLE OF CONTENTS

1	Introduction	6
2	Study Objective	6
2.1	Study Hypothesis	6
3	Study Design	7
4	Ethics Review / Statement of Compliance	7
4.1	Relevant Standards / Guidelines	7
4.2	Institutional Review Board	7
4.3	Informed Consent	7
5	Clinical Trial Registration	8
6	Potential Risks and Benefits to Human Subjects	8
7	Materials and Methods	9
7.1	Participants	9
7.2	Study Materials	10
7.3	Visit Schedule and Procedures	12
8	Adverse Event Reporting	18
8.1	Adverse Event Definitions	18
8.2	Procedures for Adverse Events	20
8.3	Reporting Adverse Events	21
8.4	Discontinuation from the Study	21
9	Device Malfunctions	21
10	Statistical Analysis	22
10.1	Sample size	22
10.2	Statistical analysis	22
11	Data Quality Assurance	22
11.1	Study monitoring	22
11.2	Record keeping	23
11.3	Record retention	23
11.4	Data Entry / Data Management	24
11.5	Confidentiality	24
11.6	Publication	24
12	Study Costs	24
13	Appendices	24
	Appendix 1	25

Appendix 230

[Redacted]

[Redacted]

3 Study Design

This will be a prospective, double-masked, randomized, bilateral, 1 week cross-over, dispensing study comparing the Invigor I DD lens against the clariti 1-day lens. Each participant will be randomized to wear either the Invigor I DD or the clariti 1-day as a matched pair first. Both study lenses will be used in a daily disposable lens wear modality for one (1) week. It is anticipated that this study will involve 3 scheduled visits:

- Visit 1: Enrollment/ Screening/ Baseline/Fitting/Dispensing of lens pair #1
- Visit 2: 1-week follow-up visit for lens pair #1 (6-10 days after dispensing pair #1), and dispensing visit of lens pair #2
- Visit 3: 1-week follow-up visit for lens pair #2 (6-10 days after lens pair #2 dispense) and exit.

4 Ethics Review / Statement of Compliance

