- i. Overall lens fit impression (-2 to 2 scale).

[REDACTED]

7. Slit lamp biomicroscopy will be assessed according to the guidelines set out in the CVI grading scales.

Lens Dispensing Pair # 2

1. There will be a break before insertion of pair 2 (of at least 10 minutes).
2. The second lens pair will be applied (according to the randomization table). The lenses will be inserted by the subject from the blister pack.
3. The use of saline for rinsing prior to insertion is permitted if necessary.

Procedures will be repeated as detailed in Visit 1 for pair 2 from section 7.3.1 (steps 2-13 in Dispensing pair#1 section).

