7.3.3 Visit 3: One Week Visit Pair 2/Study Exit

This visit will occur 6-10 days after dispense of lens pair #2.

*Subjects will be asked to wear lenses for **at least 2 hours** prior to the visit appointment.*

Subjects who attend without lenses in situ for at least two hours will be rescheduled.

Procedures for assessment of pair # 2 will be followed (similar to assessment of pair #

[REDACTED]

[REDACTED]

[REDACTED]

[REDACTED]

[REDACTED]

[REDACTED]

[REDACTED]

[figure not shown]
3. Slit lamp biomicroscopy assessment will be conducted according to the guidelines set out in the CVI Grading scales

4. Exit visual acuity with habitual spectacles or spectacle refraction (using same method and refraction as entry).
5. The subject will be discharged and will sign the exit statement.

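### Section 10.2 compares the lenses in a randomised two-period crossover by a plain paired t test with no period term; adding the term is nearly free and protects the lens contrast against a period shift.

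*Combined protocol and SAP*

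**What the plan says.** Section 3 describes a "prospective, double-masked, randomized, bilateral, 1 week cross-over, dispensing study" in which each subject is randomised to the lens worn first. For the lens contrast, section 10.2 says: "Paired t test will be used to compare slit lamp biomicroscopy, lens fit and subjective scores between study lens types". The only other model it names serves a different comparison: "Repeated Measures Analysis of Variance (ANOVA) or paired analysis will be used to compare the variables between study visits". No visible text elsewhere puts period or sequence into the lens contrast.

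The conditions before the two dispensings differ. Under section 7.3.1 the subject attends Visit 1 "not wearing their habitual contact lens products for at least 12 hours prior to the study visit". At Visit 2 (section 7.3.2) the subject arrives wearing the first lens: "Subjects who attend without lenses in situ for at least two hours will be rescheduled". Pair #2 is inserted after a break of at least 10 minutes (section 7.3 says simply 10 minutes), and then: "Procedures will be repeated as detailed in Visit 1 for pair 2 from section 7.3.1". Those repeated steps include comfort after settling and lens fit, both outcome types on the paired-t list.

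The two 1-week assessments are alike: 6 to 10 days after dispensing and at least 2 hours of wear. For Visit 3, section 7.3.3 says: "This visit will occur 6-10 days after dispense of lens pair #2".

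**The concern.** In a two-period crossover, a subject's lens difference (test minus control) contains the lens effect plus or minus the period shift, with the sign set by the sequence. A paired t test pools the two sequences as if they had the same mean. This has two consequences when a shift exists:

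- **Completers balanced by sequence.** The shift cancels from the mean difference but stays in its estimated variance. The test is unbiased and conservative, and it loses power.
- **Completers unequal by sequence.** The shift no longer cancels, and the lens estimate is biased.

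Inequality is plausible: section 10.1 expects about 70 enrolled and about 50 completing, section 7.1 does not replace discontinued subjects, and section 10.2 drops missing data points. The exposure is greatest for comfort and fit at dispensing, because the starting conditions of the two periods differ by design. At the 1-week assessments a shift is possible but not built in.

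**Working it through.** **Inputs.** From section 10.1 and Table 3: lens difference 0.5, SD of individual differences σ = 1.2, α = 0.05 (taken as two-sided), power 80%, n = 48 required, about 50 completers. Assumed because the documents do not give them: the period shift d (period 2 minus period 1), from 0 to 1.0 point, and the split of completers n1/n2.

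**The plan's own figure.** Paired t test, two-sided, n−1 df, non-central t: n = 48 gives 80.7% power and n = 47 gives 79.9%. Table 3 is reproduced. With a period term and equal sequences (n−2 df), n = 48 still gives 80.7%.

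**Model.** Within-subject lens differences are N(τ + d, σ²) in one sequence and N(τ − d, σ²) in the other.

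- *Plain paired t:* the mean difference has expectation τ + d(n1−n2)/n and true SE σ/√n. The sum of squares, divided by σ², is non-central chi-square on n−1 df with non-centrality 4d²n1n2/(nσ²). Rejection probabilities come from numerical integration.
- *Period-adjusted:* the estimate is the average of the two sequence means, with SE = (σ/2)√(1/n1 + 1/n2) and n−2 df. It does not depend on d.

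**One case by hand: 25/25, d = 0.5.** The true SE is 1.2/√50 = 0.170. The non-centrality is 4 × 0.25 × 625/(50 × 1.44) = 8.68. The expected sample variance is therefore 1.44 × (49 + 8.68)/49 = 1.695, an SD of about 1.30. The paired t test works with an SE of about 1.30/√50 = 0.184 instead of 0.170.

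**Balanced, 25/25, n = 50**

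| Shift d | Paired-t power | Power with term | Paired-t type I error |
|---|---|---|---|
| 0 | 82.3% | 82.3% | 5.0% |
| 0.1 | 82.1% | 82.3% | 4.9% |
| 0.25 | 81.2% | 82.3% | 4.5% |
| 0.5 | 77.6% | 82.3% | 3.4% |
| 1.0 | 62.6% | 82.3% | 1.1% |

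**Moderately unequal, 27/23.** The bias is 0.25 × 4/50 = 0.02 at d = 0.25 and 0.5 × 4/50 = 0.04 at d = 0.5. At d = 0.5, paired-t power is 70.2% if the bias opposes the lens effect and 83.9% if it favours it, against 82.1% with the term. Type I error is 3.9%.

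**Stress case, 30/20.** The bias is 0.5 × 10/50 = 0.10 and 1.0 × 10/50 = 0.20. Type I error is 6.6% and about 8.5%. Power in the adverse direction is 57.5% and 21.1%, against 80.7% with the term.

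**How likely are such splits?** The number randomised and any blocking are not in the visible text. With equal allocation and 50 completing at random (hypergeometric), or with unrestricted allocation (binomial):

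| Assumption | 27/23 or worse | 30/20 or worse |
|---|---|---|
| 70 randomised, 35/35 | 43% | 1.6% |
| 60 randomised, 30/30 | 30% | 0.08% |
| 54 randomised, 27/27 | 11% | 0 |
| Unrestricted allocation | 67% | 20% |

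**Second reading of the SD.** If the historical 1.2 already contains a shift of 0.5, the within-sequence SD is √(1.44 − 0.25) = 1.09. At 25/25, power is then 84.5% for the paired t test and 88.8% with the term. The gain is between 4 and 5 points on either reading.

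**The case against.** The strongest reply is that the planned test is valid under the randomisation. If loss is unrelated to sequence, the average bias is zero. Type I error averaged over the random splits is 5.0% at shifts of 0.25, 0.5 and 1.0 under unrestricted allocation, and 4.7%, 3.8% and 2.0% with 35/35 randomised. The 6.6% and 8.5% figures belong to one chosen split. This stands, and it makes the point mainly one of precision. It does not help a trial that has already finished with an unequal split, where the estimate reported is the biased one.

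Second, section 7.3.1 counts a subject as enrolled at consent, before eligibility is confirmed and a randomisation ID assigned. The 70 may therefore include screen failures, and fewer may be randomised. This also stands: under equal allocation, 43% and 1.6% are upper-end figures.

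Third, the gain depends on a shift of unknown size. At 0.25 or less with balance it is about 1 point, and a shift of 0.5 equals the whole target lens difference. Settling before the ratings may also reduce the contrast between the two dispensings, and the visible text does not allow that to be judged. This is fair, and it is why the result is given as a range.

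Fourth, one degree of freedom is the whole cost only when sequences are equal. That is correct, and the further cost is given with the fix.

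**Conclusion.** The concern holds. The lens contrast has no period term, although the design is a randomised crossover and the two dispensings start under different conditions. This is not an error in the sample size and does not make the planned test invalid. It is an avoidable loss of precision and, when completers are unequal by sequence, an avoidable bias.

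The size depends on the assumed shift. It is negligible at 0.25 or less with balanced sequences. At 0.5 the loss is about 5 power points with balance (77.6% against 82.3%, below the planned 80%), and about 12 points in the adverse direction at 27/23 (70.2% against 82.1%). Type I error rises above 5% only with marked imbalance. The change should be made because the protection costs almost nothing; confidence that it will matter in practice is moderate, since neither the shift nor the split is known.

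**What to change.** For the continuous lens comparisons in section 10.2, replace the paired t test with the standard crossover model: fixed effects for lens, period and sequence, and random subject. For subjects with both periods this is equivalent to the period-adjusted t test on within-subject differences. Specify it before unmasking, since a period term added later would be a post hoc choice. Report the number of completers in each sequence.

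The cost is wording only. The randomised sequence is already known for every subject, and no data or subjects are added. If there is no period effect, the loss of power is nothing measurable at 25/25 (82.3% either way), 0.2 to 0.3 points at 27/23 (82.1% against 82.3%), and 1.6 points at 30/20 (80.7% against 82.3%).

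Two limits remain. The term does not remove carry-over, which is a separate question, and the yes/no and short ordinal fit grades are outside this model.

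### Does the paired t test for slit-lamp and lens-fit outcomes need a stated rule for combining the two eyes?

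*Combined protocol and SAP*

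**What the plan says.** Section 3 describes a bilateral cross-over in which the same lens type is worn in both eyes at a time: "Each participant will be randomized to wear either the Invigor I DD or the clariti 1-day as a matched pair first". The randomized unit is therefore the subject.

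Section 7.3.2 (Visit 2) states that "any ocular measurement procedures outlined below will be carried out on each eye". Lens fit is graded monocularly in 7.3.1 and 7.3.2, and the 7.3.2 list also contains the slit-lamp item: "Slit lamp biomicroscopy will be assessed according to the guidelines set out in the CVI grading scales". Section 7.3.3 follows similar procedures for the second pair at Visit 3.

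Section 10.2 gives the between-lens analysis in one sentence: "Paired t test will be used to compare slit lamp biomicroscopy, lens fit and subjective scores between study lens types". It adds a repeated-measures ANOVA or paired analysis for comparisons between visits, a 0.05 significance level with multiplicity adjustment, inclusion of all evaluated participants, and exclusion of missing data points. It does not mention eyes.

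Section 10.1 counts people. It says that "a sample size of 50 completing subjects is sufficient to detect a mean difference of 0.5" in subjective ratings, and the first column of Table 3 is "Mean individual difference in score".

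**The concern.** A subject wears one lens type in both eyes, then the other type in both eyes. For post-blink movement, say, that gives a right-eye lens difference and a left-eye lens difference. The two share the same person, period, examiner and wearing habits, so they are probably positively correlated.

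A paired t test can be run at either level. Pairing removes the dependence between the two lenses; it does nothing about the dependence between the two eyes. Four readings fit the wording of 10.2:

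- average the two eyes;
- use one eye;
- test right and left eyes separately;
- enter all eyes as separate pairs.

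The last is a familiar error in ophthalmic trials. It treats 50 subjects as 100 independent observations, makes the standard error too small, and declares lens differences too often. The multiplicity adjustment lowers the threshold but does not repair the standard error, and the ANOVA sentence concerns visits, not eyes. If the plan led an analyst to that reading, the fit and slit-lamp comparisons would be unreliable.

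**Working it through.** **1. The plan's own figure.** Inputs from Table 3: mean difference 0.5, SD 1.2, alpha 0.05, power 80%. With a paired t test on one difference per subject, two-sided (noncentral t), the smallest n with at least 80% power is 48:

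- n = 47: 79.9%
- n = 48: 80.7%
- n = 50: 82.3%

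The normal approximation, ((1.96 + 0.842) × 1.2 / 0.5)² = 45.2, gives 46. Table 3 therefore reproduces with the subject as the unit.

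**2. If eyes were pooled.** Let σ be the SD of a single eye's lens difference and ρ the correlation between a subject's two eye differences. The documents give no ρ, so all values are assumed. With 50 subjects and 100 eyes:

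- naive standard error: σ/√100 = 0.100σ;
- true standard error: σ√((1 + ρ)/100), which is 0.122σ at ρ = 0.5;
- true two-sided error of a nominal 5% test: 2 × (1 − Φ(1.96/√(1 + ρ))).

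At ρ = 0.5, 1.96/1.225 = 1.60 and the error is 11.0%. The second threshold below, 0.5%, stands for a Bonferroni adjustment over an assumed 10 tests; the plan gives no count.

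| Assumed ρ | Error at nominal 5% | Error at nominal 0.5% |
|---|---|---|
| −0.2 | 2.8% | 0.2% |
| 0 | 5.0% | 0.5% |
| 0.1 | 6.2% | 0.7% |
| 0.3 | 8.6% | 1.4% |
| 0.5 | 11.0% | 2.2% |
| 0.7 | 13.3% | 3.1% |
| 1.0 | 16.6% | 4.7% |

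Simulation with normal differences (100,000 trials of 50 subjects) agrees: 11.0% at ρ = 0.5 and 16.9% at ρ = 1.0.

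**3. The other three readings.**

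- *Average the eyes.* Each subject's mean has variance σ²(1 + ρ)/2. Dividing by 50 gives σ²(1 + ρ)/100, the true variance in step 2. Simulated error is 4.9% to 5.1% for ρ from 0 to 1.
- *One eye.* The variance is σ²/50, so the test is valid but less precise. The standard error is √(2/(1 + ρ)) times the averaged one, or 1.15 at ρ = 0.5. Where averaging has 80% power, one eye has 55%, 62%, 68% and 73% at ρ = 0.1, 0.3, 0.5 and 0.7.
- *Each eye separately.* With no adjustment, the chance that at least one eye is falsely significant is about 8% to 10% for ρ from 0.1 to 0.7. The plan does adjust: two tests at 2.5% each cannot exceed 2 × 2.5% = 5%.

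**4. Which reading the text supports.** Section 3 randomizes participants, 10.1 counts completing subjects, Table 3 speaks of an individual difference, and 10.2 takes its analysis set as participants. No sentence counts eyes. Pooling is the reading with least support and the only one whose standard error is wrong.

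**The case for a change.** The best case for a change is as follows. The cues towards the subject are indirect: 10.1 sizes only the subjective ratings, and a statement about which participants are analysed does not define the unit. Even if the subject is meant, averaging and single-eye selection both remain open, and a choice made after seeing the data could affect the result. For example, a pooled-eye p-value of 0.01 corresponds to about 0.036 with averaging at ρ = 0.5. The visible text of 10.2 is unbroken, so redaction does not explain the gap. One sentence would close it, with no extra subjects or data.

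Much of this stands. The omission is real, the formula is right, and a stated unit would be tidier. It does not amount to a fault in the plan, for three reasons:

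- The harm needs an analyst to choose the one incorrect reading, against the direction of the text. The remaining choice is between valid tests that differ in precision.
- The figures illustrate and do not measure this trial. Every ρ and the count of 10 tests are assumed, and the normal model does not describe all the outcomes. Fit includes yes/no items and a three-category centration grade, and slit-lamp findings are graded. For a sparse yes/no finding (assumed prevalence 2% to 5%, latent eye correlation 0.5 to 0.7), pooled error was 5.6% to 8.7% and eye-averaged error 2.3% to 4.2%; at 10% prevalence pooled error was about 8% to 10%.
- For the same reason, a single sentence prescribing averaging and a t test for every per-eye outcome would suit the millimetre and percentage measures but not the categorical ones.

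**Conclusion.** No change to the plan follows. Section 10.2 leaves out a detail, the handling of two eyes per subject, that a competent analyst would supply by working at subject level, as the design and the sample size already do.

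Had eyes been pooled, a nominal 5% test would have run at roughly 6% to 17% for assumed positive correlations from 0.1 to 1.0, before the planned adjustment. The documents do not plan that analysis. The sample size and the subjective ratings are untouched.

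The conclusion rests on two things: no visible passage says that eyes enter as independent pairs, and none makes a fit or slit-lamp outcome primary. The objective and hypothesis text is redacted, so the second cannot be confirmed. A report that did count eyes as independent would contain an analysis error, to be raised against that report.
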